Study Protocol with Statistical Analysis Plan

Study Title

The Effectiveness of Wearable Devices on Health Promotion in Individuals with Diabetes Mellitus

Principal Investigator

[name], PT, PhD
Doctor of Physical Therapy Program
Pacific University
Email: [contact] | [contact]

Proposal to Conduct Research

Institutional Review Board FWA: 00007392 IRB: 0004173
2032697-1
IRB Number
09/14/2023
Approved
12/01/2023
Post-Approval Request(s)
09/14/2024
Approval Expires

1. Study Objectives

This randomized controlled pilot study aims to evaluate the effectiveness of wrist-worn activity trackers (Fitbit Inspire 2) on improving physical activity levels, cardiovascular risk factors, and quality of life in adults diagnosed with type 2 diabetes over a 4-week period.

2. Study Design

- Type: Interventional (Clinical Trial), two-arm parallel design
- Randomization: Yes (1:1 allocation)
- Blinding: None
- Duration: 4 weeks
- Sample Size: 20 participants (10 per group)

3. Eligibility Criteria

Inclusion Criteria:

- Age \geq 18 years
- Diagnosed with type 2 diabetes (HbA1c \geq 6.5% or fasting glucose \geq 126 mg/dL)
- Willing and able to link a fitness tracker app to a smartphone

Exclusion Criteria:

- Use of assistive devices for walking
- Current smokers
- Pregnant or breastfeeding
- Already achieving \geq 150 min/week of moderate-to-vigorous activity
- Comorbidities preventing participation in physical activity
- Current insulin therapy

4. Intervention and Control Groups

Intervention Group: Participants receive a Fitbit Inspire 2.

Control Group: Participants do not receive a wearable device.

5. Outcome Measures

Primary Outcomes:

- Physical activity: Measured using Global Physical Activity Questionnaire (GPAQ) and pedometer/mobile app data
- Cardiovascular risk: Measured using arterial stiffness (SphygmoCor), blood pressure, heart rate, fasting glucose, BMI, waist-to-hip ratio

Secondary Outcomes:

- Health-related quality of life: Measured using the RAND SF-36 Health Survey

6. Statistical Analysis

Descriptive statistics will summarize baseline characteristics. Non-parametric tests will be used:

- Friedman's test and Wilcoxon signed-rank tests (within-group change)
- Mann-Whitney U test (between-group comparison)
- Spearman's rho for correlations

Effect sizes (r) will be calculated. All analyses will be conducted using IBM SPSS v29. Significance set at $p < 0.05$.

7. Data Management and Confidentiality

Data will be stored in a secure BOX folder regulated by the PI. No identifiable data will be stored on local or personal devices. Data will be retained for five years post-study.

8. Risks and Benefits

Risks: Minimal; primarily related to fasting and physical exertion.

Benefits: Participants may gain insight into their physical activity levels and cardiovascular health.

Compensation: None, though participants in the intervention group may retain their Fitbit upon study completion.

9. Ethical Considerations

IRB Approval: Pacific University IRB #2032697-1

Informed consent is obtained electronically via Qualtrics in English or Spanish. No deception is used. Adverse events will be monitored and reported per IRB policy.

10. Timeline

- Recruitment: Upon IRB approval
- Data Collection: Week 0 (T0) and Week 4 (T1)
- Analysis & Dissemination: Expected completion within 3 months post-data collection

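### Section 5 lists eight primary measures and Section 6 ranks neither the measures nor the tests, so a within-arm change or one chance result could be reported as a positive primary finding

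*Combined protocol and SAP*

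**What the plan says.** Section 1 states the aim: "This randomized controlled pilot study aims to evaluate the effectiveness of wrist-worn activity trackers". Section 2 describes a two-arm parallel trial with 1:1 randomisation, 10 participants per group and "Blinding: None".

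Section 5 has two primary domains. Physical activity is "Measured using Global Physical Activity Questionnaire (GPAQ) and pedometer/mobile app data", which is two measures. The second domain reads "Cardiovascular risk: Measured using arterial stiffness (SphygmoCor), blood pressure, heart rate, fasting glucose, BMI, waist-to-hip ratio", which is six measures if blood pressure is counted once. Only quality of life is secondary.

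Section 6 lists Friedman's test and "Wilcoxon signed-rank tests (within-group change"), then "Mann-Whitney U test (between-group comparison"), then Spearman correlations and effect sizes (r). One threshold covers them all: "Significance set at $p < 0.05". The section does not identify a deciding measure or comparison, rank the tests, adjust for multiplicity or call any analysis exploratory. It also does not say whether the between-group test uses week-4 values or change from baseline. Section 10 gives two time points, T0 and T1 (week 4).

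**The concern.** Two things are left open for a trial whose stated aim is effectiveness.

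- **Which comparison decides.** The within-group tests stand beside the between-group test with no order of importance. In an unblinded trial, a pre-post change in the tracker arm alone does not show a device effect, because it does not use the randomised control group. The plan as written does not rule out reporting such a change as the primary result.
- **Which measure decides.** Eight measures share primary status at an unadjusted 0.05. If one of them reached significance, the plan would not tell a reader whether that measure was the intended test or one of eight chances.

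The stake is how the result can be interpreted. The plan makes no power claim, and nothing here affects the conduct of visits or participant safety.

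**Working it through.** **The plan's own figure.** There is none to reproduce. The plan states no familywise error rate, and the sample size of 20 has no derivation.

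**Inputs from the documents.** Eight primary measures (2 + 6, Section 5); Mann-Whitney as the between-group test and a 0.05 threshold (Section 6); 10 v 10 (Section 2); one follow-up visit (Section 10).

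**Assumptions added here.** Two-sided tests, one between-group test per measure, no ties, all 20 participants analysed, and no device effect on any measure. Any one significant between-group test is read as success; this rule is not in the plan. The documents give no correlations, so a range is shown. Within-group tests are not counted, because they address a different null hypothesis.

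**Step 1: true size of one test.** For 10 v 10, U has mean 50 and SD √(10 × 10 × 21/12) = 13.23.

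- Exact p-values: the test rejects at U ≤ 23, with size 0.0433.
- Asymptotic p-values without continuity correction: U = 24 gives z = (24 − 50)/13.23 = −1.965 and p = 0.0494, so it also rejects. The true size is 0.0524.

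**Step 2: eight independent tests**, 1 − (1 − size)^8.

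- Exact: 1 − 0.9567^8 = 0.298.
- Asymptotic: 1 − 0.9476^8 = 0.350.

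**Step 3: eight correlated tests.** Simulation of equally correlated normal outcomes, 400,000 trials per cell:

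| Pairwise correlation | Exact | Asymptotic |
|---|---|---|
| 0.3 | 27.1% | 31.8% |
| 0.5 | 23.4% | 27.4% |
| 0.7 | 18.5% | 21.6% |
| 0.9 | 11.8% | 13.9% |

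With correlation 0.7 within each domain and 0 between domains, the results are 22% exact and 26% asymptotic.

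**Step 4: sensitivity to the count and to dropout.**

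- Seven tests, if pedometer/app data cannot be compared between arms: exact 26.6% if independent, 11.3% at correlation 0.9.
- Nine tests, if systolic and diastolic pressure are separate: asymptotic 38.4% if independent.
- Seven to nine tests together therefore span about 11% to 38%.
- Eight independent tests, exact / asymptotic: 28% / 34% at 9 v 9, and 34% / 34% at 8 v 8.

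**Step 5: with two named primaries and Holm.** The smaller p-value must meet 0.05/2 = 0.025. At 10 v 10 that means U ≤ 20 under either type of p-value, with size 0.0232. If the two tests are independent, 1 − (1 − 0.0232)^2 = 0.046. At correlation 0.7 the simulated figure is 0.041.

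**The case against.** The strongest reply is that this is a 20-person pilot with no power claim and no confirmatory decision rule, and that familywise control is not automatically required of such a study. Section 6 also commits to effect sizes, so p-values are not the only planned output. This limits the consequence. It does not remove the point, because Section 1 gives effectiveness as the aim, with no feasibility aim, and Section 6 sets a significance threshold without calling anything exploratory.

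A second reply is that in a randomised two-arm design the Mann-Whitney comparison is the natural test of effectiveness, so the within-group tests are unlikely to be misread. That is a fair softening, but the plan does not say it.

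Three stronger readings are tempting, and the documents do not support them.

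- A reader might infer that the plan has a false-positive rate of 12% to 35%. It has no stated rate, because it has no success rule. That range also covers only the eight-test count, and its low end needs measures as different as a questionnaire and waist-to-hip ratio to correlate at 0.9.
- A reader might infer from "Control Group: Participants do not receive a wearable device" that controls supply no pedometer or app data. Section 5 also allows pedometer and mobile app sources, and the plan does not say how they are collected in each arm. Seven tests is therefore only a possible reading.
- A reader might infer that a formal multiplicity adjustment is the only remedy. For a pilot of this size, declaring all outcomes exploratory is equally valid.

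**Conclusion.** The concern holds as an omission that should be fixed. The plan gives eight measures primary status and does not say which measure or which comparison decides effectiveness. The gap over the comparison matters at least as much as the count, because it leaves room for an uncontrolled pre-post change to stand as evidence of effectiveness.

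The size is illustrative and rests on a success rule assumed here. For eight tests it is most plausibly in the range of about 22% to 35%, which covers independence, correlation up to 0.5 and the two-domain structure. At correlation 0.9 throughout it falls to about 12% to 14%. Every case computed is more than twice 5%, so the conclusion does not depend on the correlation chosen. The upper end is not a limit: splitting a measure into components would add tests.

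**What to change.** **1. In Section 6, rank the comparisons.** State that the between-group comparison of the T0-to-T1 change is the primary comparison, and that within-group tests are descriptive and are not evidence of effectiveness.

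**2. Then choose one option.**

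- **(a) Before outcome data are examined:** name in Section 5 one primary measure per domain, each collected the same way in both arms. Apply Holm adjustment at 0.05 across the two between-group tests, and label all other measures secondary or exploratory. Pedometer/app data qualify only if controls supply them in the same way. If GPAQ is chosen, state that it is self-reported in an unblinded trial, so reporting bias can affect that result.
- **(b) At any stage:** label all outcomes of this pilot exploratory, report every measure now listed as primary with an effect estimate and 95% confidence interval, and make no claim of effectiveness from individual p-values.

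The documents do not say whether outcome data have been examined. If they have, only (b) applies, because a primary measure chosen at that point could be chosen on its result.

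**Cost.** Wording in Sections 5 and 6, with no new data or visits; an IRB amendment may be needed. Fewer results can be called significant: under (a) the smaller of the two p-values must meet 0.025, and under (b) no individual p-value supports a claim of effectiveness.

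### The only between-group test leaves out T0 and does not name its variable; for near-normal outcomes, ANCOVA with T0 as covariate would be more precise

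*Combined protocol and SAP*

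**What the plan says.** Section 6 (Statistical Analysis) opts for non-parametric methods throughout. Its only between-arm entry is "Mann-Whitney U test (between-group comparison". No variable, covariate, model or transformation is named. The idea of change appears only in the within-arm entry, "Wilcoxon signed-rank tests (within-group change". For baseline the section says "Descriptive statistics will summarize baseline characteristics". The effect measure is covered by "Effect sizes (r) will be calculated", and no confidence interval is mentioned. SPSS v29 is named, but not whether the Mann-Whitney p-value is exact or asymptotic.

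Section 10 (Timeline) schedules both measurements: "Data Collection: Week 0 (T0) and Week 4 (T1". Section 2 (Study Design) gives "Sample Size: 20 participants (10 per group".

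**The concern.** Two analysts could follow Section 6 faithfully and run different main tests, one on T1 and one on T1 minus T0. Which of the two has more power depends on the T0-T1 correlation, which the documents do not give.

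Both readings also use T0 inefficiently. A test on T1 ignores it. A test on change subtracts it with a fixed weight of 1, whatever the correlation. ANCOVA estimates the weight from the data. With 20 participants, information already scheduled for collection should not be left out of the comparison that randomisation supports.

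The planned effect size r is unit-free and comes without an interval. It gives no difference in blood pressure, glucose or activity minutes that could be used to plan a larger trial.

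**Working it through.** **Inputs from the documents.** 10 per arm (Section 2), threshold 0.05 (Section 6; two-sided assumed), measurements at T0 and T1 (Section 10). The sample size of 20 cannot be reproduced, because no effect, SD, power or dropout is given.

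**Assumed inputs.** T0-T1 correlation ρ from 0 to 0.9; true effect mainly 1.0 SD; equal variances.

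**Step 1: variance of the between-arm difference, relative to T1 alone.**
- T1 only: 1
- Change: 2(1 − ρ)
- ANCOVA: (1 − ρ²) × [1 + 1/(N − 4)] = (1 − ρ²) × 1.0625 at N = 20, the factor being the price of estimating the slope

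| ρ | 0 | 0.3 | 0.5 | 0.7 | 0.8 | 0.9 |
|---|---|---|---|---|---|---|
| SE, ANCOVA / T1 | 1.03 | 0.98 | 0.89 | 0.74 | 0.62 | 0.45 |
| SE, ANCOVA / change | 0.73 | 0.83 | 0.89 | 0.95 | 0.98 | 1.005 |

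Break-even with T1: 1.0625(1 − ρ²) = 1, so ρ ≈ 0.24. Break-even with change: 1.0625(1 + ρ) = 2, so ρ ≈ 0.88. Outside that range ANCOVA loses at most about 3% of the SE.

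**Step 2: power by simulation, normal data, 1.0 SD effect.** The exact Mann-Whitney rejects at U ≤ 23 or U ≥ 77, a true level of 4.3%. The asymptotic version, without continuity correction, has a level of 5.1 to 5.4%. ANCOVA uses t on 17 df; its simulated level was 4.9 to 5.3%.

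| ρ | 0 | 0.3 | 0.5 | 0.7 | 0.8 | 0.9 |
|---|---|---|---|---|---|---|
| Exact Mann-Whitney, T1 (%) | 51 | 51 | 51 | 51 | 51 | 51 |
| Exact Mann-Whitney, change (%) | 28 | 39 | 51 | 73 | 89 | 99 |
| Asymptotic, better reading (%) | 55 | 55 | 55 | 76 | 90 | 99.6 |
| ANCOVA (%) | 54 | 58 | 66 | 82 | 93 | 99.6 |
| Gain over better exact (points) | 2 to 3 | 6 to 7 | 14 | 8 | 4 | 0 |
| Gain over better asymptotic (points) | −1 | 3 | 11 | 5 | 2 | 0 |

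Gains are taken before rounding. The better reading is known only if ρ is known. Against the worse exact reading the gap is 58 − 39 = 19 points at ρ = 0.3 and 93 − 51 = 42 points at ρ = 0.8.

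At 0.5 SD every method is underpowered. At ρ = 0.3/0.5/0.7/0.8 ANCOVA has 19/22/30/40%, against 16/16/24/34% for the better exact reading.

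**Step 3: interval width.** Half-widths in SD units at ρ = 0.3/0.5/0.7/0.8:
- ANCOVA: 0.91/0.83/0.68/0.57
- Hodges-Lehmann on T1: 0.98 throughout
- Hodges-Lehmann on change: 1.16/0.98/0.77/0.62

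The Hodges-Lehmann intervals cover 95 to 96%, so they are slightly conservative.

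**Step 4: does the choice of variable matter?** At 1.0 SD, exact Mann-Whitney on T1 and on change give different verdicts in 33/35/40/45% of trials at ρ = 0.3/0.5/0.7/0.8. Under no effect this is about 7 to 8%.

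**Step 5: where the ordering fails.** For lognormal data (log-SD 1, shift 1 on the log scale), at the same four correlations:
- Raw-scale ANCOVA: 37/42/55/67%
- Better exact Mann-Whitney: 51/54/73/86%
- Log-scale ANCOVA: 58/66/82/93%
- Rank ANCOVA: 56/62/76/87%

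On normal data, rank ANCOVA has 55/62/76/87% against 51/51/73/89% for the better exact Mann-Whitney. That is clearly ahead near 0.5 and slightly behind at 0.8.

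**The case against.** The strongest reply is that Mann-Whitney is valid and defensible at 10 per arm, that the team chose non-parametric methods deliberately for a small pilot, and that naming the variable would be repair enough. Much of this stands.
- The test is valid. A reader might infer that leaving T0 out biases the result; under randomisation it does not.
- Part of the gain over the exact test comes from its 4.3% level. Against an asymptotic test the gain at ρ = 0.3 to 0.8 is about 2 to 11 points.
- Rank ANCOVA yields no adjusted interval and loses to Mann-Whitney on change at high correlation. It should therefore be confined to outcomes that need it.
- Every correlation and effect size here is assumed.

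What does not stand is that naming the variable is enough. It removes the ambiguity but still commits the team to a guess about ρ, and it provides no adjusted estimate with an interval.

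Other stronger readings are not supported:
- *T0 is used only descriptively.* It also enters the within-group tests. What it lacks is a stated role between groups.
- *ANCOVA always wins.* Step 5 shows otherwise.
- *The exclusion of people already at "150 min/week of moderate-to-vigorous activity" caps GPAQ at T0 and so lowers its correlation with T1.* Section 3 does not say that this criterion is assessed by GPAQ.
- *The team will report whichever reading is significant.* That would raise the null rejection rate to about 8%, but nothing in the documents says it is planned.

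**Conclusion.** The point holds as a matter of precision and prespecification. Section 6 has a valid but unadjusted between-group test, on a variable it does not name, with an effect measure that has neither units nor an interval.

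For near-normal or suitably transformed outcomes at a 1.0 SD effect and assumed correlations of 0.3 to 0.8, ANCOVA gains about 2 to 14 points of power over the better Mann-Whitney reading, depending on the correlation and on the version of the test. The gain is about 0 at correlation 0.9, and between −1 and +3 at correlation 0. On strongly skewed raw data Mann-Whitney is the better test. The documents give no distribution for any outcome, so the scale has to be decided outcome by outcome. The change is worth making, but the trial's validity does not depend on it.

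**What to change.** Replace the Mann-Whitney line in Section 6 with text to this effect:

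*For each outcome with a T0 value, the between-group estimate is from ANCOVA of T1 on arm with T0 as covariate, on a raw or log scale fixed for that outcome before any T1 data are seen, reported as an adjusted difference (or ratio) with 95% CI. For outcomes expected to be heavily skewed or to have many zeros, such as GPAQ, the p-value is from rank ANCOVA, and an unadjusted Hodges-Lehmann difference on T1 with its CI is given as description. Mann-Whitney U on T1 is the sensitivity analysis.*

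Section 5 defines physical activity as "Measured using Global Physical Activity Questionnaire (GPAQ) and pedometer/mobile app data", without saying whether the pedometer or app data will include a T0 value. If they do not, Mann-Whitney on T1 should be the main test for them. If the team prefers to keep Mann-Whitney as the main test throughout, Section 6 should at least name its variable for each outcome and say whether the p-value is exact or asymptotic.

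The cost is a few sentences and a short table of scales, with no new data where T0 exists. ANCOVA adds a linearity assumption and uses one degree of freedom, making the CI about 3% wider at correlation 0. Rank ANCOVA has less power than Mann-Whitney on change at correlations of about 0.8 or more (87 against 89% at 0.8 and 1.0 SD; 52 against 61% at 0.9 and 0.5 SD). Main and sensitivity tests can disagree: rank ANCOVA and Mann-Whitney on T1 do so in about 10 to 38% of trials at 1.0 SD. The plan should therefore state in advance which result is primary.

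### Section 6 commits to one treatment-effect measure, an undefined r with no outcome units and no interval, so the size and precision of the between-group difference need not be reported

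*Combined protocol and SAP*

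**What the plan says.** Section 2 of the combined protocol and SAP gives the size of this two-arm trial as "Sample Size: 20 participants (10 per group", allocated 1:1. Section 1 calls it a pilot and sets out to assess whether the device works. Most primary outcomes in section 5 have natural units, such as blood pressure, heart rate, fasting glucose and BMI. Section 10 places data collection at week 0 (T0) and week 4 (T1).

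The whole analysis plan is in section 6:

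- Between arms: "Mann-Whitney U test (between-group comparison".
- Within arms: "Friedman's test and Wilcoxon signed-rank tests (within-group change".
- Association: "Spearman's rho for correlations", with no variables named. This does not estimate a treatment effect.
- Description: "Descriptive statistics will summarize baseline characteristics". No follow-up summary is mentioned.
- Effect measure: "Effect sizes (r) will be calculated".

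The significance threshold is 0.05, with sidedness not stated. No section names a mean or median difference, a change expressed in outcome units, a confidence interval or any other measure of precision. No formula is given for r, and the N that would enter it is not identified.

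**The concern.** A trial with 10 participants per arm will seldom settle effectiveness by a significance test. Its useful output is an estimate of the between-group difference and an honest statement of how uncertain that estimate is. The plan promises a test and a unit-free r. Under either common definition, r comes from the same rank statistic as the p-value, so the second number adds little to the first.

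Two things are at stake. First, someone planning a later trial would have no difference in blood pressure, glucose or activity to work from. Second, a reader who sees a non-significant p and its r could not tell a result that rules out a worthwhile difference from one that is merely imprecise.

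**Working it through.** **The plan's own figure.** Only 10 + 10 = 20 can be checked. No power, target difference, SD or dropout allowance is given, so the sample size cannot be derived.

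**Inputs.** From section 2: 10 per arm. From section 6: the Mann-Whitney test and a 0.05 threshold. Assumed: two-sided testing, complete data, no ties, and r equal either to Z/√N or to the rank-biserial correlation.

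**Step 1: r as a function of the test statistic.** Let U be the smaller Mann-Whitney count. Without ties its null mean is 10 × 10 / 2 = 50 and its null variance is 10 × 10 × 21 / 12 = 175. Then

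- Z = (50 − U)/√175
- r = Z/√20 = (50 − U)/√3500 = (50 − U)/59.16
- rank-biserial r = 1 − 2U/100 = (50 − U)/50

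Both versions are fixed multiples of 50 − U, and the exact two-sided p is also determined by U:

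| U | exact p | Z | Z/√20 | rank-biserial |
|---|---|---|---|---|
| 40 | 0.481 | 0.756 | 0.169 | 0.20 |
| 30 | 0.143 | 1.512 | 0.338 | 0.40 |
| 24 | 0.0524 | 1.965 | 0.439 | 0.52 |
| 23 | 0.0433 | 2.041 | 0.456 | 0.54 |
| 10 | 0.0015 | 3.024 | 0.676 | 0.80 |
| 0 | 0.00001 | 3.780 | 0.845 | 1.00 |

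Each row has one p and one absolute r. Exact p < 0.05 is the same event as Z/√20 of at least 0.456. Complete separation of the arms gives 50/59.16 = 0.845, the ceiling for that version.

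**Step 2: r carries no units.** One simulated 10 v 10 data set gave p = 0.070 and r = 0.406, with a Hodges-Lehmann difference of 0.37 (interval −0.13 to 1.10). Multiplying every value by 100 left p and r unchanged, while the difference became 36.6 (−13.1 to 110.1).

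**Step 3: what an interval would show.** The Hodges-Lehmann estimate is the median of the 100 pairwise between-arm differences. The interval that inverts the Mann-Whitney test runs from the 24th to the 77th ordered difference, because U ≤ 23 is the exact rejection region. Its coverage without ties is 1 − 0.0433 = 95.7%. In 20,000 simulated trials with normal data and equal SDs, its mean half-width was 0.98 SD (0.9845), so the full width is 2 × 0.9845 = 1.97 SD. As a rough check, a t-interval with the SD set at its true value has half-width 0.94 SD. The documents give no SD, so these figures cannot be turned into mmHg or mg/dL.

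**The case against.** The strongest reply is that section 6 is a short list of methods and forbids nothing. Medians, differences and intervals could all appear in the report. That is correct. A reader might infer that the trial will report no effect in outcome units and no uncertainty, but the text supports only that the plan makes no commitment to do so.

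A reader might also infer, without qualification, that r merely repeats the p-value. The documents do not define r, so this is conditional. A signed r gives direction, which a two-sided p does not, and a rank-biserial r can be read as a difference in probabilities of superiority. Ties, plausible in questionnaire scores, loosen the mapping. Losses shift it: p = 0.05 by the normal approximation corresponds to r = 0.438 at N = 20, 0.462 at N = 18 and 0.490 at N = 16. The proposed interval is tied to the test as well, since it excludes zero exactly when the test rejects. Its advantage is units and visible width.

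Two further arguments are tempting and should not be used:

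- That r cannot separate a null effect from a large one, because r is sizeable in every significant result. That comes from selecting on significance, and section 6 does not restrict r to significant outcomes. Without selection, mean r in simulation is 0.00, 0.23 and 0.44 at true differences of 0, 0.5 and 1 SD. With selection, the mean absolute Hodges-Lehmann estimate is inflated too: 0.97, 1.12 and 1.32 SD.
- That r within an arm will be set against r between arms on a different scale. Nothing in the documents plans such a comparison. What stands is that r and its N need a definition.

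**Conclusion.** The point holds as a gap in planned estimation. The only treatment-effect measure to which section 6 commits is undefined, has no outcome units and comes with no interval. That much follows directly from the text.

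The link between r and p is conditional on r being Z/√N or rank-biserial, with 10 per arm, complete data and no ties. The half-width of about 0.98 SD rests on normal data with equal SDs and is an average over simulated trials. It shows the scale of what would go unreported: even an observed difference of zero would typically leave differences of nearly one SD in either direction within the interval.

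The planned tests are not invalidated and trial conduct is unaffected. The change should be made because a pilot's value lies in the quantity that the plan omits.

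**What to change.** Replace the effect-size sentence in section 6 with:

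> For every outcome, whether or not the test is significant, the between-group difference in change from T0 to T1 will be reported in the units of that outcome as the Hodges-Lehmann estimate, with the 95% confidence interval that inverts the Mann-Whitney test applied to the same changes. Conclusions will be based on this interval. Any r reported is supplementary, with its formula and N stated.

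This wording also settles something section 6 leaves open: whether the Mann-Whitney test is applied to changes or to week-4 values. The sponsor should make that choice deliberately, and the test and the estimate must use the same quantity. The SAP should add that the interval has 95.7% coverage at 10 per arm without ties and is approximate with ties, and that reading the estimate as a location shift assumes similarly shaped distributions in the two arms, which is doubtful for self-reported activity.

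The cost is a few lines of text and a little more analysis, using data already planned for collection. The intervals will be wide and the results will look less decisive, which is an accurate picture of what 20 participants can show.
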